5.8.3 Patient Global Assessment (PGA)

The PGA scale consists of a simple judgement indicating improvement, no change, or worsening since the start of the study and is documented after 12 months (visit 3) and at visit 5 (24 months) on a 7 point Likert scale (1="very much improved" to 4="unchanged" to 7="very much worsened").

The self-reported patient global assessment (PGA) will be displayed by numbers and percentages by visit (after 1 year and, if sufficient data are available, after 2 years), treatment group and in total.

5.8.4 Patient Health Questionnaire (PHQ-9)

Change in depression measure by the Patient Health Questionnaire (PHQ-9D = validated German version of the PHQ-9) between baseline and 365 days (main secondary outcome) and between baseline and 730 days (other secondary outcome). The PHQ-9D will be filled out at screening, visit 3 (after 12 months) and visit 5 (after 24 months). The PHQ-9D is a self-administered version of the PRIME-MD diagnostic instrument common mental disorders. The PHQ-9 is the depression module, which scores each of the 9 DSM-IV criteria. It has been validated for use in primary care. The PHQ-9D questionnaire will be analysed by assigning 0 point for the category “never”, 1 point for the category “at some days”, 2 points for the category “at more than 50% of the days” and 3 points for the category “nearly every day”. The total score will be calculated building the sum of all items and therefore ranges between 0 and 27. The cut-off for signs of depression was set at a PHQ-9 score of ≥ 10 .

5.8.5 Self-estimated adherence

The self-estimated adherence is documented at visit 1, 3, and 5 on a scale from 0 to 100 percent in 5 % steps and absolute values by visit and changes will be analysed between baseline and visit 3, and visit 5, respectively.

5.9 Secondary safety variables

The following secondary safety outcomes will be evaluated during 365-days follow-up according to the primary safety variables:

- Percentage of days lost due to unplanned cardiovascular (CV) hospitalizations or all-cause death
- All-cause mortality or unplanned cardiovascular hospitalizations as recurrent event (number)
- Unplanned cardiovascular hospitalizations (recurrent event, number)
- Unplanned hospitalizations for heart failure (recurrent event, number)
- Days lost due to hospitalizations of any cause or death
- Percentage of days lost due to hospitalizations of any cause or death of any cause
- Unplanned all-cause hospitalizations
- All-cause mortality

The following secondary safety outcomes will be evaluated during the patient's individual time within study (=individual follow-up time):

- All-cause mortality or unplanned cardiovascular hospitalizations as recurrent event (number)
- Unplanned cardiovascular hospitalizations (recurrent event, number)
- Unplanned hospitalizations for heart failure (recurrent event, number)
- Percentage of days lost due to unplanned cardiovascular hospitalizations
- Percentage of days lost due to hospitalizations of any cause
- Unplanned all-cause hospitalizations

- All-cause mortality

Table 5 Secondary safety variables - Definition of patients' individual follow-up time

	Intervention group (IG) and control group (CG)
ITT	From randomization until end of study. End of study: 
 - 31.12.2016 - If date of visit 6 or last visit in 2017: 31.12.2016 - If date of final study visit before 30.06.2016: Date of visit 6 - Death: date of death - Withdrawal of informed consent: date of withdrawal - Premature termination of study: date of premature termination

The percentage of days lost due to hospitalisation will be calculated as the ratio of the sum of the number of days lost due to stays in hospital during the respective patient follow-up time and the respective patient follow-up time, expressed in percent.

For days lost due to unplanned cardiovascular hospitalizations, the admission und discharge day will be counted as one day. Calculations will be done in days.

5.10 Other variables

5.10.1 Adverse events

Apart from hospitalizations and deaths no further adverse events are specifically collected within this study.

5.10.2 Laboratory parameters

The following laboratory parameters will be documented at visit 1, 3, and 5:

- HbA1c [%]
- Potassium [mmol/l]
- Creatinine [mg/dl]
- Total cholesterol [mg/dl] and [mmol/l]
- HDL-cholesterol [mg/dl] and [mmol/l]
- LDL-cholesterol [mg/dl] and [mmol/l]
- Triglycerides [mg/dl] and [mmol/l]
- BNP [pg/ml], if available
- NT-proBNP [pg/ml], if available
- Urea [mg/dl]

5.10.3 Vital signs

The following vital signs will be documented at visit 1, 3, and 5:

- Systolic blood pressure [mmHg]
- Diastolic blood pressure [mmHg]
- Pulse [/min]

5.10.4 Documentation of intervention

5.10.4.1 Medication review

DRP (drug-related problems)

Pharmacists detected possible DRP in the medication review at the first patient interview after inclusion (intervention group only). They used a brown bag review and existing pharmacy patient records for information on current medication. They compared these sources with the medication plan provided by the recruiting physician (eCRF). For a standardized procedure, pharmacists used a checklist to identify and document possible DRP. Omission and commission of drugs, other deviations in dosing regimen, duplications, interactions, contraindications, adverse drug reactions (ADR), non-adherence, problems in drug handling, splitting of tablets that must not be split, and “others” were defined as DRP in this study. The pharmacists aimed to solve the DRP and document the result of the intervention. Throughout the study, pharmacists documented DRP continuously. The documented DRP will be classified by the Department of Medicine, ABDA.

Discrepancies

Deviations between physician’s medication plan (eCRF), pharmacist’s brown bag interview (paper based) and first consolidated medication plan (eCRF) were defined as discrepancies. Those include in particular omissions and commissions of drugs, mixing up intended long-term and as needed (PRN) use as well as non-exclusive deviations in frequency, number of units, timing of administration and drug strength. Discrepancies will be identified and classified by the Department of Medicine, ABDA.

5.10.4.2 Weekly pharmacy visits

In the intervention group, the patient visits weekly or biweekly the pharmacy to collect their prepared medication. In case a collection by the patient or a relative was not possible, pharmacists documented the reason and delivered the medications to the patient’s home, if appropriate. Pharmacists were required to ask the patient several health-related questions to record possible changes and to identify a need for an (immediate) doctor’s visit. Content was the health status, newly developed symptoms, decrease in performance, adherence to medication regimen, changes in weight or blood pressure and pulse.

The following parameters will be assessed:

- The choice of weekly or biweekly visits
- Number and percentage of weeks where medication was dispensed
- The way patient got medication (at the pharmacy, delivered at home, got medication in advance, not dispensed due to hospitalization, not dispensed due to stay at nursing home, not dispensed due to other reasons, patient died)
- Consultation of physician is recommended (yes, no, could not be assessed)

- Direct consultation of the physician performed (yes, no, could not be assessed)
- Reason for consultation (chest pain, dyspnoea, oedema, change of performance, dizziness/faint, extra systole, pulse, blood pressure, non-adherence, drug related problems (DRP), other).
- Changes of the medication plan

5.10.4.3 Survey on satisfaction of participating physicians and pharmacists

Participating physicians and pharmacists completed a survey on different aspects of PHARM-CHF after the study. They were asked to evaluate the study and the cooperation between physician and pharmacist within the study.

6 Missing values and outliers

6.1 Missing values

No substitution of missing values will be done.

6.2 Outliers

No methods for detection of outliers will be employed.

7 Statistical analyses

Categorical variables will be presented by numbers and percentages. If not otherwise stated, the missing values will be shown as an additional missing category and the percentages will be calculated based on all non-missing values.

Continuous variables will be summarised by the descriptive statistics n, mean, standard deviation, minimum, 25%-quartile, median, 75%-quartile and maximum.

All variables will be shown for each treatment group and in total.

All variables documented in the eCRF will be provided by patient in Excel datasheets.

7.1 Timing of final analysis

When all data from the eCRF, the data processing centres and the health insurance funds will be collected, study data will be prepared for determination of the PDC. Afterwards the final analyses will be performed.

Estimated timing of final analysis: February 2019

All outcomes will be analysed collectively.

7.2 **Patient disposition**

The following patient disposition variables will be presented by numbers and percentages for the total, ITT and the PP population:

- Randomized
- Major protocol violations (with details listed)
- Deaths
- Discontinued except death (with reasons listed)
- Time within the study (≥ 12 months) of the patients who died
- Time within the study (≥ 12 months) of the patients who discontinued except death
- Time within the study of all patients

365 days follow-up

- Terminated prematurely
 - Withdrawal of informed consent
 - Discontinuation
- Death
- Completed first 365 days of study

Follow-up between 365 and 730 days:

- Terminated prematurely
 - Withdrawal of informed consent
 - Discontinuation
- Death
- Study duration < 730 days
- Completed 730 days of study

The following patient disposition variables will be presented by sample characteristics for the total, ITT and the PP population:

- Number of events
- Number of unplanned cardiovascular hospitalizations
- Number of unplanned cardiovascular hospitalizations (365 days)
- Number of events per patient
- Time within the study of the patients who died
- Time within the study who discontinued except death
- Time within study overall
- Time within study of patients who terminated the study regularly

The participation on visit 1, visit 3, and visit 5 as well as the possible reason for drop out will be tabulated for the ITT.

The individual duration of study will be calculated for each patient by duration = (date of end of study – date of randomization) + 1 and will be analysed descriptively.

7.3 Adherence to intervention

The exposure will only be assessed for the intervention group by counting the weekly visits at the pharmacies if patient got medication. Hospital stays and the choice of weekly and biweekly visits will be considered. The number of visits at the pharmacy and the number of visits at the pharmacy per duration of study in weeks will be tabulated for the intervention group.

7.4 Participating physicians and pharmacies

The number of pharmacies, physicians and patients per study region, the number of patients per pharmacy and physician and the number of physicians per specialist's group will be tabulated.

7.5 Demographics and patient characteristics

The following variables will be presented for ITT and the PP population.

7.5.1 Demographics

All variables mentioned in chapter 5.3 will be tabulated.

Exploratory p-values of the Chi-Square test on differences between the treatment groups will be shown for categorical variables. They will be interpreted on a significance level of 5%.

Exploratory p-values of the t-test on differences between treatment groups assuming unequal variances will be shown for continuous variables. They will be interpreted on a significance level of 5%.

7.5.2 Patient characteristics

All variables mentioned in chapter 5.3 will be tabulated for the baseline visit. If variables will also be collected at subsequent visits, the variables will also be displayed by visit (e.g. laboratory parameters and vital signs).

Exploratory p-values of the Chi-Square test on differences between the treatment groups will be shown for categorical variables. They will be interpreted on a significance level of 5%.

Exploratory p-values of the t-test on differences between treatment groups assuming unequal variances will be shown for continuous variables. They will be interpreted on a significance level of 5%.

7.6 Medication therapy

The following variables will be presented for ITT and the PP population.

7.6.1 Medication therapy documented by physicians and pharmacists

Medication therapy will be presented by numbers and percentages. Drug substances will be coded in the most current version according to WHO ATC.

Medication therapy will be provided by ATC 2 and 4 levels for the medication plan provided by the recruiting physician (eCRF, at baseline, after 12 months, and after 24 months), the first consolidated medication plan (intervention group) and the medication plan documented by the pharmacy over time (intervention group).

Medication therapy will be provided by ATC level 5 for medicines belonging to the ATC code 1st level C ('cardiovascular system') provided by the recruiting physician (eCRF at Baseline, after 12 months, and after 24 months) and the first consolidated medication plan (intervention group).

The number of brand products (drug packages like Aspirin® or RAMIPRIL comp-CT® 5 mg/25 mg), the number of drug classes (level 4, distinct ATC-codes), the number of drug substances (counting each drug substance of fixed combinations: e.g., RAMIPRIL comp-CT® 5 mg/25 mg = 2 drug substances i.e. ramipril and hydrochlorothiazide), the number of single doses per day and the number of drug intakes per day (e.g. morning, noon, evening, at night) will be presented for data provided by the physician (eCRF at baseline, after 12 months, and after 24 months) and first consolidated medication plan (intervention group).

Number of single doses per day counts every intake of a brand product per day per patient. Number of intakes per day counts, how often the patient takes medicine per day.

For the ATC code 1st level C (cardiovascular system) the number of brand products (drug packages like Aspirin® or RAMIPRIL comp-CT® 5 mg/25 mg), the number of drug classes (level 4, distinct ATC-codes), the number of drug substances (counting each drug substance of fixed combinations: e.g., RAMIPRIL comp-CT® 5 mg/25 mg = 2 drug substances), the number of single doses per day and the number of drug intakes per day (e.g. morning, noon evening, at night) will be presented for data provided by the physician (eCRF at baseline, after 12 months and after 24 months) and first consolidated medication plan (intervention group).

For heart failure medication (ACEi/ARB, BB, MRA and their combinations) and lipid modifying agents (statins, others) the dosage per day (baseline, visit 3, and visit 5) in DDD and the changes between visit 1, 3, and 5 (new medications, stopped medications, changes regarding strength and dosage, number of single doses) and one versus half a tablet (splitting) will be presented.

7.6.2 Pharmacy claims data

The number of patients with data from data processing centres (Apothekenrechenzentren) and data from statutory health insurance (SHI) funds will be analysed.

7.7 Hospitalization during study participation

Events regarding hospitalization are recorded in the medical practices (eCRF) and will be provided by health insurance funds. The number of events provided by medical practices and provided by health insurance funds will be tabulated. The number of events adjudicated as unplanned hospitalization by the CEC will be compared between the two sources. For patients with both data sources, the amount of underreporting will be calculated.

7.8 Primary efficacy analysis

The primary efficacy analysis is the analysis of the PDC between baseline (day of randomization) and 365 days. The pharmacy claims data will be provided by data processing centres and health insurance funds. However, health insurance data were not available for all patients included in the study. Differences between patients with data from data processing centres and data from health insurance funds cannot be excluded. Therefore, an analysis will be performed comparing the data from health insurance funds and data processing centres. The analysis will be conducted twice. On the one hand, the analysis will be adjusted for data from health insurance funds (yes/no). And on the other hand, the analysis will be adjusted for data from health insurance funds (yes/no) and for baseline adherence (yes/no).

Analysis adjusted for data from health insurance funds only

The PDC (adjusted for data from health insurance funds only) will be analysed by a two-sided stratified Wilcoxon signed-rank test (van Elteren test) on a two-sided level of significance of 5%. The level of significance will not be divided among further hypotheses.

The following hypothesis will be tested:

$H_0: m_i = m_c$ vs. $H_1: m_i \neq m_c$,

Where m_i denotes the median value of the intervention group and m_c denotes the median value of the control group.

The following SAS code can be used:

```
proc freq data=xxx;  
    table updated*treatment group*PDC / cmh scores=modridit noprint;  
run;
```

Analysis adjusted for data from health insurance funds and baseline adherence

The PDC (adjusted for data from health insurance funds and baseline adherence) will be analysed by an analysis of covariance (ANCOVA). Treatment group will serve as a fixed effect and baseline adherence will serve as a random effect. Treatment groups will be compared on a two-sided level of significance of 5%. The level of significance will not be divided among further hypotheses.

The following hypothesis will be tested:

H0: $\mu_i = \mu_C$ vs. H1: $\mu_i \neq \mu_C$,

Where μ_i denotes the mean value of the intervention group and μ_C denotes the mean value of the control group.

The primary analysis population for both adjustment types is the ITT population. However, the primary analysis (both adjustments) will be repeated for the PP population for sensitivity. As a further sensitivity analysis an analysis of (co)variance (AN(C)OVA) for the PDC will be done with PDC as dependent variable, and the further fixed effects treatment (intervention vs. control), data from health insurance funds (yes/no), sex (male vs. female), age (≤ 75 vs. > 75 years), NYHA functional class (I and II vs. III and IV), PHQ-9 score (score < 10 vs. ≥ 10) and diabetes mellitus (yes vs. no). The study region will be omitted since this may lead to an over determination of the analysis model.

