### **11.4.1 Primary Efficacy Analysis**

The primary efficacy analysis is the analysis of the PDC for three CHF medications (ACEi/ARB, BB and MRA). The pharmacy claims data are provided by data processing centres and health insurance funds. If health insurance data are not available for all patients, an analysis will be performed comparing the data from health insurance funds and data processing centres. The analysis will be adjusted for data from health insurance funds (yes/no).

The PDC will be analysed by a two-sided stratified Wilcoxon signed-rank test (van Elteren test) on a two-sided level of significance of 5%.

The following hypothesis will be tested:

$H_0: m_i = m_c$  vs.  $H_1: m_i \neq m_c$ ,

Where  $m_i$  denotes the median value of the intervention group and  $m_c$  denotes the median value of the control group.

Although statistical guidelines ("Points to consider on adjustment for baseline covariates") suggest adjusting the analysis for all stratification variables of the randomization process, this is omitted. It is desired to get a robust result, if one treatment regimen is favourable to the other across all stratification factors. Nevertheless, supportive analyses adjusting for the stratification factors will be conducted as sensitivity analyses.

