Table 4 PDC analyses - definition for 365 days' follow-up

	Intervention group (IG) and control group (CG)
ITT	Version 1) From randomization until 365 days following the randomization If a patient dies: the sum of days between randomization and date of death Version 2) If a patient discontinues within 365 days: the sum of days between randomization and discontinuation

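### SAP 7.8 replaces the protocol's single primary efficacy test with two, each at the full 5% and with no rule for which decides, so the family-wise error exceeds 5%

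*SAP*

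**What the plan says.** Protocol 11.4.1 names one primary efficacy test: "The PDC will be analysed by a two-sided stratified Wilcoxon signed-rank test (van Elteren test) on a two-sided level of significance of 5" per cent, adjusted for whether health-insurance data are available. The only other adjusted analyses there use the randomization factors, and the protocol calls them sensitivity analyses. The sample size (Protocol 11.1, SAP 1.2) assumes one test at 5%; SAP 1.2 specifies a two-sided t-test.

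SAP 7.8 says "The analysis will be conducted twice" and sets out:

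- a van Elteren test comparing medians, stratified by insurance-data availability, at a two-sided 5% level;
- an ANCOVA comparing means, which adds baseline adherence, and for which "Treatment groups will be compared on a two-sided level of significance of 5" per cent.

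Under each of the two stands the sentence "The level of significance will not be divided among further hypotheses". The section then says "The primary analysis population for both adjustment types is the ITT population" and that "the primary analysis (both adjustments) will be repeated for the PP population for sensitivity". Only the per-protocol repeat and a further model with the minimization factors are labelled sensitivity analyses.

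Table 4 in SAP 5.6 also lists two versions of the 365-day PDC. Version 2 reads "If a patient discontinues within 365 days: the sum of days between randomization and discontinuation". The table does not say which version is primary.

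**The concern.** Two tests of the same endpoint, each at the full 5% and each called primary, give two chances of a false positive. The sentence about not dividing the level does not help: it stands under both tests, so each receives the whole 5%.

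The SAP does not say which test decides, whether both must succeed, or how to read a split result such as p = 0.07 on one and p = 0.04 on the other. This is the only endpoint the trial is powered for (Protocol 11.1). Whether it is reported as met could depend on which result is put forward after the data are seen.

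The second test is also loosely specified. SAP 7.8 describes baseline adherence as a yes/no variable in one place and as a random effect in another, and the sentence listing the model effects omits the insurance-data term. That leaves further room for choice.

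**Working it through.** **1. The plan's own design figure.** Inputs (SAP 1.2): difference 0.10, SD 0.22, two-sided alpha 0.05, power 85%.

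- Normal approximation: n per arm = 2 × (1.960 + 1.036)² × 0.22² / 0.10² = 86.9, so 87.
- Exact two-sided t-test: 87.9, so 88 per arm and 176 in total, with power 85.05%. This reproduces the stated figure.
- With 30% dropout, 176 / 0.70 = 251.4, so 252. The stated 248 is within 3% of that.

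The design therefore rests on one test at 5%.

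**2. Bounds on the error with two tests.** If a significant result on either test counts:

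- independent tests: 1 − 0.95² = 9.75%;
- upper bound for any dependence: 0.05 + 0.05 = 10%.

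The two tests share the same PDC data and are positively correlated, so the true figure lies below these bounds. It follows from P(either) = P(first) + P(second) − P(both).

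**3. Simulation under no effect.** The ITT sizes of 110 and 127 come from SAP Table 2. The documents do not give the correlation between baseline and follow-up PDC or the share of patients with insurance data. The correlation is therefore varied, and 70% is assumed for the share. Baseline adherence is fitted as an ordinary fixed covariate alongside the insurance stratum.

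*Beta-distributed PDC, mean 0.70, SD 0.22, 20,000 trials per setting.* The chance that at least one test is significant is 6.7% (r = 0.3), 7.7% (r = 0.5) and 8.5% (r = 0.7). Each test alone gives 4.9% to 5.2%.

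*Other shapes and covariate forms, 10,000 trials per setting.* Here r is the correlation of the underlying normal variables, and the yes/no covariate is cut at 0.80. The chance that at least one test is significant is:

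| Baseline adherence | PDC shape | r = 0 | 0.3 | 0.5 | 0.7 | 0.8 |
|---|---|---|---|---|---|---|
| continuous | capped normal | 5.9% | 6.5% | 7.4% | 8.1% | 8.6% |
| continuous | left-skewed | 6.6% | 7.0% | 7.6% | 8.3% | 9.4% |
| yes/no | capped normal | 5.6% | 6.4% | 6.5% | 7.9% | 8.4% |
| yes/no | left-skewed | 6.7% | 7.1% | 8.1% | 8.4% | 8.9% |

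Monte Carlo error is about 0.2 to 0.3 points. In these runs each test alone gave 4.4% to 5.5%, and both were significant together in 1.1% to 4.3%. Worked example (continuous, capped normal, r = 0.5): 4.99% + 5.08% − 2.71% = 7.36%.

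The error rises with r because a strong baseline covariate removes variance from the ANCOVA but not from the van Elteren test, so the two disagree more often.

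**4. Table 4.** Of the 10 ITT patients who terminated within twelve months (SAP Table 3), 7 withdrew consent and have no PDC (SAP 5.5). Only the other 3 can have a PDC that differs between Versions 1 and 2, so the two versions add little to the error.

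**The case against.** The best defence is that the protocol already settles the matter. It names the van Elteren test and leaves only detailed methodology to the SAP, so relying on the ANCOVA alone would be a visible departure. This has weight as a reason for choosing the van Elteren test in the fix. But the SAP is the more detailed document, calls both analyses primary, and does not say that the protocol's test prevails.

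A second argument is that the error is inflated only if success on either test may be claimed. If both had to succeed, the error would fall to about 1% to 4%. That is true, but the SAP states no such rule. Family-wise error is the chance of at least one false rejection, and as written each rejection stands on its own at 5%.

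A third is that the size is modest and depends on assumptions: the correlation and the 70% share are not in the documents, and the simulated ANCOVA does not treat baseline adherence as random. This stands as a limit on precision. It does not change the direction: the error was above 5% in every setting examined, including a yes/no baseline covariate and zero correlation.

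Finally, Version 2 in Table 4 may be only a handling rule for early discontinuation. With 3 patients affected, it is a point of clarity and not a main source of error.

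**Conclusion.** The point holds, and it should be fixed before the final analysis. One protocol test at 5% has become two analyses in the SAP, both called primary, each at an undivided 5% and with no decision rule. A claim that the primary efficacy endpoint was met at 5% is therefore not controlled at 5%.

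The chance of at least one false positive is 6.7% to 8.5% for assumed correlations of 0.3 to 0.7, and about 5.6% to 9.4% over the wider set of assumptions. The 9.75% for independent tests is only a reference bound. These figures assume that about 70% of patients have insurance data, that every ITT patient has a PDC, and that baseline adherence enters as an ordinary covariate.

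**What to change.** State in SAP 7.8 that the only confirmatory test is the protocol's van Elteren test of the 365-day summary PDC (Table 4, Version 1), stratified by insurance-data availability, at two-sided 5%. Label the baseline-adjusted ANCOVA and Version 2 as supportive, and report the ANCOVA as an adjusted mean difference with its 95% confidence interval. In the same edit, say whether baseline adherence is continuous or yes/no, how it enters the model, and that the insurance-data term is included.

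Two alternatives also control the error:

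- a fixed sequence, in which the second test is confirmatory only if the first succeeds;
- the ANCOVA alone as confirmatory. This conflicts with Protocol 11.4.1 and would need a protocol amendment as well.

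Naming one test or fixing a sequence leaves 176 and 248 unchanged. The main fix costs two sentences, plus the clarification of the ANCOVA, and gives up one route to a positive primary result.

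Keeping both tests as primary at 0.025 each costs more. The t-test calculation then gives 105.3, so 106 per arm, 212 in total, and 212 / 0.70 = 302.9, so 303 enrolled. Power at the planned 88 per arm would fall to 77.4%. With the ITT numbers less the consent withdrawals in SAP Table 3 (110 − 6 = 104 and 127 − 1 = 126), it would be 87.9%.

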1.1 Objectives

The aim of PHARM-CHF is to investigate, whether a continuous interdisciplinary intervention improves medication adherence (primary efficacy variable of interest) and leads to a reduction of hospitalizations and mortality (primary safety variable of interest) in elderly patients with CHF.

The primary efficacy variable is medication adherence to cardiovascular medication, pre-specified as a significant difference of the proportion of days covered (PDC) between the intervention and control group within 365 days following randomization measured by pharmacy claims data.

The primary safety variable is days lost due to blindly adjudicated unplanned cardiovascular hospitalizations or death of any cause.

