7.9 Primary safety analysis

The primary safety variable is all-cause mortality or unplanned cardiovascular hospitalizations as number of days lost due to unplanned cardiovascular hospitalizations or death between baseline (day of randomization) and 365 days.

The percentage of days lost due to death of any cause or unplanned cardiovascular hospitalizations as the fraction of maximum possible days alive and out of hospital will be analysed by a Wilcoxon signed-rank test comparing both treatment groups. Additionally, the number of days lost due to death of any cause or unplanned cardiovascular hospitalizations will be analysed descriptively by treatment group and in total.

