7.10 Secondary analyses

All parameters will be tested for the ITT population on a two-sided level of significance 5%. All p-values will be interpreted in an exploratory way.

All secondary variables will also be analysed for the PP population. These analyses will be considered as exploratory only.

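### No decision rule links the two primary variables: PDC is tested at an undivided 5%, while days lost is tested as primary with no level, order or exploratory label

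*SAP*

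**What the plan says.** **Two primary variables.** SAP 1.1 sets out two. First: "The primary efficacy variable is medication adherence to cardiovascular medication", expressed as a difference in PDC between groups over 365 days. The second aim is whether the intervention "leads to a reduction of hospitalizations and mortality (primary safety variable of interest) in elderly patients with CHF", and the variable is defined in the same section: "The primary safety variable is days lost due to blindly adjudicated unplanned cardiovascular hospitalizations or death of any cause". It is labelled safety, but the stated aim is a benefit.

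**PDC.** SAP 7.8 and Protocol 11.4.1 give null and alternative hypotheses and a two-sided 5% level. SAP 7.8 states "The analysis will be conducted twice": once as a van Elteren test and once as an ANCOVA that also adjusts for baseline adherence. Under each it says "The level of significance will not be divided among further hypotheses". It then refers to both as the primary analysis. Protocol 11.4.1 has only the van Elteren test in that role.

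**Days lost.** SAP 7.9 begins "The primary safety variable is all-cause mortality or unplanned cardiovascular hospitalizations as number of days lost" and compares the groups with a Wilcoxon test. Protocol 11.4.2 does the same. Neither gives hypotheses, a significance level, sidedness, a place in an order, or an exploratory label.

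**Exploratory label.** SAP 7.10 says of the secondary analyses: "All p-values will be interpreted in an exploratory way". Subgroup analyses (SAP 7.11), secondary safety variables and per-protocol analyses (Protocol 11.4.4) are labelled in the same way. SAP 7.9 is not.

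**Power.** Protocol 11.1 says that the sample size serves the efficacy variable alone.

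**The concern.** Two variables are called primary, both are tested between groups, and both carry a hope of benefit. A reader cannot tell what counts as a positive trial: PDC alone, either variable, or both.

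As written, PDC could fail, days lost could reach a nominal p-value below 0.05, and the second result could be reported as a positive primary outcome without departing from the plan. That claim would come from a test for which the trial was not sized and which has no stated error rate.

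The status of days lost is blurred further by its form. SAP 7.9 applies the test to the percentage of days lost over 365 days, and SAP 5.9 lists that same percentage among the secondary safety variables. Whether the exploratory label in SAP 7.10 reaches the test in SAP 7.9 is therefore unclear.

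**Working it through.** **1. The plan's own figure.** Inputs from SAP 1.2: difference 0.10, SD 0.22, two-sided alpha 5%, power 85%, t-test.
- Normal approximation: n per group = 2 × (1.960 + 1.036)² × (0.22/0.10)² = 86.9, so 87.
- t-test: 87.88, so 88 per group and N = 176. Power at 88 per group is 85.05%.

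The stated 176 is reproduced. It uses the whole 5% for one PDC test.

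**2. Either result may be claimed.** Assumptions that are not in the documents: days lost is also tested at two-sided 5%, either result alone counts as success, and both null hypotheses are true.
- Independent tests: 1 − (1 − 0.05)² = 1 − 0.9025 = 9.75%.
- Any dependence at all: at most 0.05 + 0.05 = 10%.
- Jointly normal test statistics, by correlation (assumed, since the documents give none):

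| Correlation | Chance of at least one false positive |
|---|---|
| 0 | 9.75% |
| 0.1 | 9.72% |
| 0.3 | 9.51% |
| 0.5 | 9.08% |
| 0.8 | 7.81% |

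**3. Other rules that the text allows.**
- PDC is the only confirmatory hypothesis: 5% for a single PDC test.
- Both must be significant: 0.05 × 0.05 = 0.25% if independent with both nulls true, and never above 5%.

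Neither rule adds inflation through the second variable.

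**4. The PDC step itself.** Any order that starts with PDC needs a single PDC test. If either the van Elteren test or the ANCOVA may open the way, that step alone runs at 7.8% (assumed correlation 0.8) or 7.0% (0.9) when PDC does not differ.

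**5. Remedies compared.**
- *Fixed order, one PDC test first.* If the PDC null is true, any false claim requires that test to reject: at most 5%. If PDC truly differs, the only possible false claim is on days lost, at 5%. The total is held at 5% and the PDC test keeps 85% power at 88 per group.
- *Equal split, 2.5% each.* Independent tests: 1 − 0.975² = 4.94%. PDC power at 88 per group falls from 85.0% to 77.4%; restoring 85% needs 106 per group (N = 212). At the ITT sizes in SAP Table 2 (110 and 127), power under the planning assumptions is 93.5% at 5% and 89.1% at 2.5%. These two are upper figures, because SAP 5.5 says that PDC cannot be calculated after withdrawal of consent.

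**The case against.** The strongest reply is that the plan has only one confirmatory hypothesis. Formal hypotheses and a 5% level appear for PDC and nowhere else, the sample size serves PDC alone, and the sentence about not dividing the level stands in the PDC section. It reads naturally as keeping the full 5% for PDC because nothing else is to be confirmed. The aim also joins the two variables with *and*, which would fit a rule that both must succeed. In addition, hospitalisations and deaths are the only adverse events collected (Protocol 12; SAP 5.4.1), so the safety label has substance, and whether one efficacy and one safety variable belong to one error family is partly a matter of judgement.

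Most of this stands. A reader might infer that the plan runs a 9.75% error rate. The documents do not support that: they give days lost no level, and they do not say that either result suffices. Nor does low power for days lost raise its false-positive rate.

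What the reply does not supply is the rule itself. Powering for one variable settles the sample size, not the standing of the other test. The both-must-succeed reading fits poorly with powering only one of the two. And the plan labels p-values exploratory in several other places, so the absence of that label from a test called primary leaves its status open.

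**Conclusion.** The concern holds as an unstated decision rule, not as a demonstrated error rate. The 9.75% is what follows if days lost is tested at 5%, either result may be claimed, the tests are independent and both nulls are true. Positive correlation lowers it moderately, to about 9.1% at 0.5 and 7.8% at 0.8; 10% is the limit without any assumption on dependence. It is the chance of at least one false-positive primary result, not the chance that a given claim is false. On the two other readings the second variable adds nothing.

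The related gap, two PDC tests both treated as primary, has to be closed in the same step, because an order that begins with PDC does not secure 5% while either test may count. This is an inexpensive improvement worth making, and it does not invalidate the planned PDC analysis.

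**What to change.** In SAP 7.8 and 7.9 and in Protocol 11.4, state that:

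1. The van Elteren test, the only primary PDC test in Protocol 11.4.1, is the decisive PDC test at two-sided 5%. The ANCOVA is supportive.
2. Days lost is confirmatory at two-sided 5% only if the van Elteren test is significant; otherwise its p-value is exploratory. The same sentence should say whether the number or the percentage of days lost is tested, since Protocol 11.4.2 and SAP 7.9 differ.

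The change should be made before any comparison of the groups is seen. It costs one or two sentences per document, takes no alpha from PDC, and leaves N (176 evaluable, 248 enrolled) and PDC power as planned. The price is that a significant days-lost or ANCOVA result after a failed van Elteren test cannot be called confirmatory. If the sponsor never meant days lost to be confirmatory, labelling its p-value exploratory in SAP 7.9 and Protocol 11.4.2 would settle that part at the same cost; the single decisive PDC test would still have to be named.
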